## **5 STUDY DESIGN AND COURSE OF STUDY**

### **5.1 General Study Design and Justification of the Design**

This is a pilot study of healthy volunteers, open label, and single center. We will use a parallel assignment of Arm A and B without masking (open label). Allocation is non-randomized, we will start with group A, followed by group B.

If we see promising results, we will plan a prospective clinical trial in patients undergoing hip arthroplasty surgery.

[figure not shown]
The intended procedures are PDT on the first day followed by skin swabbing for control of skin microbiome of treated area immediately after PDT (day 0) and after 1, 3 and 5 days of PDT to analyze how long the effect lasts.

We think that this study design with healthy volunteers is adequate before starting a clinical trial.

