Objective(s):	The overarching aim of this research project is to prevent orthopedic implant-associated infections. This study aims to investigate if PDT has an effect on bacterial skin colonization in order to improve skin antisepsis strategies for the prevention of surgical site infections.  In a previous pilot study, we investigated if skin antisepsis is improved with previous PDT with the photosensitizer-inducing prodrug 5% topical methyl aminolevulinate (MAL) on inguinal skin in 10 participants. The induced photosensitizer was protoporphyrin IX (Pp IX, 635 nm) activated by red light. We showed a complete sterilization of colonizing skin bacteria at the same day after this treatment. However, orthopedic surgeons are hesitant to perform an arthroplasty surgery after such a treatment due to skin erythema for a few days.  We are entirely convinced about this novel prevention concept but need to identify the photosensitizer with the ideal balance of bactericidal effect versus skin irritation. Building upon the data we gathered, we will explore PDT with the two photosensitizers MAL and Methylene blue with potentially less local side-effects (skin erythema).

Outcome(s):	
Primary outcome:  Effect of photodynamic treatment with the photosensitizers Pp IX (MAL) and Methylene blue in combination with surgical antisepsis on bacterial skin colonization on the day of application and on day 1, 3, and 5
 
Secondary outcome:  Effect of PDT on the skin microbiome using molecular techniques.

Study design:	Pilot study, open label, single center

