## 2.4 Justification of Study Intervention

PDT enjoys great popularity as it is well tolerated. Therefore, we select this promising treatment to investigate an innovative strategy to improve skin antisepsis in a pilot study. If we see that we have sterile cultures after PDT and skin antisepsis without side effects, we will plan a larger prospective study based on these data.

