## 2.7 Study Population

Twenty healthy male and female volunteers'  $\geq 18$  years will be recruited for this clinical study. The first ten enrolled participants will be allocated to receive MAL (group A), the other ten participants will receive Methylene blue (group B). The type of PDT (group A and B) is not blinded to both participant and study investigator. The study will be approved by the local ethical committee and conducted with a study nurse and a doctoral thesis student (to be determined) in collaboration with the Clinic for Dermatology at the University Hospital Zurich, and with the Institute of Medical Microbiology at the University of Zurich. An informed consent will be obtained from each participant. We will exclude pregnant and lactating women, participants taking antibiotics in the 14 days prior to the PDT or until follow-up at 21 days, participants who received oral retinoid therapy within the last 6 months, participants who received anti-inflammatory agents within the 14 days prior and after the photodynamic treatment, participants taking any photosensitizing drugs within 4 weeks prior to the photodynamic treatment, participants who had a history of photosensitivity disorder or having a Fitzpatrick's skin phototype V-V (16).

We will not include vulnerable participants. There will be a financial compensation (value CHF 50.00) to the participants as in the previous trial (PHOMIC) was asked by the ethical committee.

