### **3.2 Primary Objective**

In this study we aim to investigate if PDT with MAL or methylene blue has an effect on bacterial skin colonization and decreases number of colonizing bacteria to improve skin antisepsis strategies for the prevention of surgical site infections.

In a previous pilot study, we investigated if skin antisepsis can be improved with previous PDT with MAL-induced Pp IX on inguinal skin in 10 participants. We showed a complete sterilization of colonizing skin bacteria at the same day after this treatment. However, orthopedic surgeons are hesitant to perform an arthroplastic surgery after such a treatment due to skin erythema for a few days.

We are entirely convinced about this novel prevention concept but need to identify the optimal irradiation source and the photosensitizer with the ideal balance of antibacterial effect versus skin irritation.

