## 10 STATISTICAL METHODS

Categorical data will be tested for differences using Fisher's exact or chi-squared tests, as appropriate, whereas continuous variables will be tested using Wilcoxon rank sum tests.

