### 10.3 Planned Analyses

- As a pilot study, we plan to do descriptive statistics only.
- Categorical data will be tested for differences using Fisher's exact or chi-squared tests.
- Continuous variables will be tested using Wilcoxon rank sum tests.
- Data will be analyzed using Stata® version 14.2 (Stata Corporation, College Station, TX). Two-tailed P-values <0.05 are considered statistically significant.

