#### 10.3.2 Primary Analysis

Descriptive comparisons of microbiological data before and after PDT by [name]

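### The control-groin passages conflict and, read literally, 7.1.2 leaves group B with no antisepsis-only control; a direct A-B comparison, if one is made, is confounded with enrolment order and light source

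*Combined protocol and SAP*

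**What the plan says.** Allocation follows enrolment order. Section 5.1: "Allocation is non-randomized, we will start with group A, followed by group B". Section 2.7: "The first ten enrolled participants will be allocated to receive MAL (group A), the other ten participants will receive Methylene blue (group B". Section 5.1 also calls this a parallel, open-label assignment.

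The primary analysis in 10.3.2 is "Descriptive comparisons of microbiological data before and after PDT". The condition for a larger study (2.4) is "sterile cultures after PDT and skin antisepsis without side effects". Neither sets A against B. The Synopsis, however, gives the motivation as "need to identify the photosensitizer with the ideal balance of bactericidal effect versus skin irritation", and 3.2 widens it to "need to identify the optimal irradiation source and the photosensitizer with the ideal balance of antibacterial effect versus skin irritation".

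Section 10.3 promises descriptive statistics only, but the same list names Fisher or chi-squared tests and a threshold: "Two-tailed P-values <0.05 are considered statistically significant". Section 10 adds that "continuous variables will be tested using Wilcoxon rank sum tests". No passage says which groups are tested.

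The untreated contralateral groin serves as the antisepsis-only control. The Synopsis, 2.5, 5.2 and 7.1.2 do not agree on who provides it. In 5.2, MAL is paired with daylight and methylene blue with a red LED.

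**The concern.** The contralateral groin is the only comparison that separates PDT plus antisepsis from antisepsis alone. If 7.1.2 is followed literally, that comparison is missing for everyone treated with methylene blue, whether or not the arms are ever compared.

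The second issue arises if the arms are compared in order to choose a photosensitizer. Arm and enrolment half are then one variable, so anything that changes between the first and second ten participants (who volunteers, how swabs are taken, how plates are graded) can appear as a photosensitizer effect. Redness is the more exposed outcome. It is recorded as yes/no items, open label, after PDT only (4.3), and has no untreated reference.

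Third, 3.2 asks for a conclusion about light that the two arms cannot supply. The results are meant to inform a trial in hip arthroplasty patients, so these limits matter for what is carried forward.

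**Working it through.** **Sample size.** 10 + 10 = 20, as in 10.2. No effect size, event rate or power is given, so nothing further can be reproduced.

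**1. Control groins.** Under 2.7, ranks 1-10 are A and ranks 11-20 are B.

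| Place | Who provides the control groin | A | B |
|---|---|---|---|
| 5.2, study schedule | all participants | 10 | 10 |
| 5.2, Figure 1 footnote | same people as the PDT group, no limit | 10 | 10 |
| 2.5 | same people, no limit | 10 | 10 |
| Synopsis | 10 participants, not said which | 10 in total | |
| 7.1.2 | the first 10 | 10 | 0 |

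**2. Arm and enrolment order.** With an intercept, arm and enrolment half as columns, the design matrix has rank 2 of 3, so the two effects cannot be estimated separately from a direct comparison. For a step change after rank k:

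share passed into A-B = (share of B enrolled after k) − (share of A enrolled after k)

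- Stated rule, k = 10: 10/10 − 0/10 = 1.0.
- k = 5: 10/10 − 5/10 = 0.5. k = 15: 5/10 − 0/10 = 0.5.
- Linear drift from rank 1 to 20: the mean ranks are 5.5 and 15.5, so 10/19 = 53% of the total drift passes through.
- Five random blocks of 4 (6^5 = 7,776 sequences), k = 10: 0 in 5,184 (66.7%), +0.2 in 1,296 and −0.2 in 1,296. The maximum absolute value at any k is 0.2.

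Illustration with assumed drifts of 10, 20 or 30 percentage points in sterile cultures. The spurious A-B difference is 10, 20 or 30 points for a step at mid-enrolment, 5, 10 or 15 for a step at rank 5 or 15, and at most 2, 4 or 6 (mean 0) with blocks of 4.

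**3. Effect on a test, if one were run.** Two-sided Fisher, 10 v 10, no true arm difference, step at mid-enrolment, all culture-positive rates assumed:

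| Early / late rate | P<0.05, sequential | P<0.05, 5 + 5 per half |
|---|---|---|
| 0.3 / 0.3 | 1.2% | 1.2% |
| 0.3 / 0.5 | 5.5% | 1.1% |
| 0.3 / 0.7 | 24.3% | 0.7% |
| 0.2 / 0.8 | 63.5% | 0.2% |

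**4. Light.** Two photosensitizers and two light sources make 2 × 2 = 4 combinations, of which 2 are studied. The matrix of intercept, photosensitizer and light also has rank 2 of 3.

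**5. Precision per arm** (Clopper-Pearson, 95%). For 10/10 sterile the lower limit is 0.025^(1/10) = 0.692, giving 69% to 100%. For 0/10 with a side effect the upper limit is 1 − 0.025^(1/10) = 0.308, giving 0% to 31%.

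**The case against.** The strongest reply is that this is an openly non-randomised, open-label pilot whose named analysis is within-person. The Synopsis and 10.3 call the statistics descriptive, and the criterion in 2.4 can be judged arm by arm. That stands. A reader might infer that sequential filling undermines the primary analysis, but it does not. The before/after and treated-versus-contralateral contrasts are made within each person.

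A reader might also infer that an A-B test is planned. None is named. It is only left open, because the listed tests are unpaired and suit two separate groups better than repeated swabs from one person.

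Nor does it follow that an A-B difference in growth is beyond repair. Baseline swabs, and contralateral swabs if taken in both arms, can remove a change shared by both groins. They cannot remove a change in PDT delivery, and redness has no such reference. No passage shows that any drift occurred, and a step at exactly mid-enrolment is the worst case.

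It is tempting to add that consecutive participant numbers (12.2) reveal the arm to the plate reader. The documents do not support this. No passage says that swab labels carry the number, 12.6 provides for encoded labels on biological material, and 12.3 provides for control of results by an uninvolved microbiologist.

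On light, 2.1 and 2.6 present daylight MAL as a follow-on to the earlier red-light pilot. That is a fair rationale, but it gives only a historical contrast.

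Randomising would not cure imprecision. If one arm is 10/10 sterile, Fisher reaches P<0.05 only at 5/10 or fewer in the other (p = 0.033; 6/10 gives 0.087). Nor would it separate photosensitizer from light.

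**Conclusion.** The point holds within these limits.

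- The control-groin conflict is a plain inconsistency and needs no assumption beyond reading 7.1.2 literally: 10 v 0 instead of 10 v 10.
- The confounding of arm with enrolment order is complete for a direct A-B comparison and irrelevant to the named analysis. Its size in practice is unknown, because every drift figure above is assumed. Between half and all of a single step change between ranks 5 and 15 would pass through.
- The best light source cannot be identified from the two combinations studied.

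The design remains legitimate as a pilot. What should change is the control-groin text and what may be claimed from an A-B difference.

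**What to change.** 1. Amend the Synopsis and 7.1.2 to match 5.2, so that contralateral control swabs are taken in all 20 participants. If 10 had been intended, this adds control sampling in 20 − 10 = 10 people already enrolled.
2. Allocate A:B 1:1 at random in small blocks, for example five blocks of 4, with the list held by someone who does not enrol. The number of participants and visits is unchanged. The downsides are that both photosensitizers and both light set-ups must be available throughout recruitment, and that the last allocation in a block can be guessed in an open-label study. If sequential filling is kept, run no A-B significance test, state that A-B differences are not interpretable as photosensitizer effects, and report each arm alone with exact 95% intervals. That needs wording only.
3. In 3.2, delete the aim of finding the best irradiation source, or state that photosensitizer plus light is tested as one package. Wording only.
4. Confirm that the encoded labels used at plate reading hide arm, side and time point.
5. Separately, the Appendix 1 example form for MAL PDT names a lamp and a dose, whereas the group A descriptions in 5.2, 8.1 and 8.3.2 specify daylight. These passages must be reconciled.

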## **5.2 Study Duration and Study Schedule**

The expected duration of participant's participation is 6 days from first study visit to the last follow-up time to report side effects of photodynamic treatment. The screening visit can be any time before but at least 1 week before the first study visit. The study schedule is indicated below.

**Figure 1.** Flow chart of the study\*

\*Visit 2 must be within 24 hours after photodynamic treatment

\*\* same participants as in the PDT group but swabs and skin antisepsis on the contralateral leg site

At the screening visit, the voluntary participant will be informed and asked for signing the informed consent by [name]. This visit and the last visit will be at the outpatient clinic for Infectious Diseases at the University Hospital Zurich. Demographic data (age, sex, current medications, and underlying diseases) will be noted.

Appointments for the photodynamic treatment (day 0) and the control visits (day 1, 3 and 5) will be made.

### Study schedule:

#### Group A (MAL group):

On day 0, a skin scraping of the groin will be performed and sent for microbiological culture. Then, 5% topical methyl aminolevulinate (MAL) as the prodrug for the photosensitizer Pp IX will be applied (5 x 10cm in the right groin) and the photodynamic process will be started by irradiation of the area with day light source.

#### Group B (Methylene blue group)

On day 0, a skin scraping of the groin will be performed and sent for microbiological culture. Then, 5ml of the 0.01% methylene blue based photosensitizer (NF-031) will be applied for an area of 5 x 10cm in the right groin of the patient. Immediately after application, the photodynamic process will be started by irradiation of the area with 40J/cm^2 red light from a 635nm (absorption peak 670nm) emitting LED during 4 minutes.

Immediately after the PDT, skin antisepsis will be performed. Antisepsis of the skin is performed with a povidone-iodine/alcohol solution (Betaseptic®, Mundipharma, Limburg, Germany) and repeated three times for a total duration of 3 minutes to imitate standard surgical antisepsis before a hip arthroplasty surgery. Skin scraping will be repeated after the antisepsis and after 1, 3 and 5 days for bacterial cultures.

As a control group, we will take skin swabs before and after skin antisepsis without PDT on the contralateral site of all participants.

On day 5 of the study, volunteers will be seen for the last study visit to document any adverse effects.

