## 2.5 Explanation for Choice of Comparator Intervention

We will use for our control group without PDT the contralateral groin of the same participants (no further participants needed).

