### 7.1.2 Control Intervention

Skin antisepsis without PDT on the contralateral site of the first 10 participants

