## Photodynamic treatment

### Group A (MAL group):

On day 0, a skin scraping of the groin will be performed and sent for microbiological culture. Then, 5% topical methyl aminolevulinate (MAL) as the prodrug for the photosensitizer Pp IX will be applied under occlusion in the right groin of the patient. After the incubation, the PDT will be started by irradiation of the area with day-light.

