### **8.3.2 Visit 1 = Day 0 of the study**

#### Group A (MAL group):

On day 0 with [name], a skin scraping of the groin will be performed and sent for microbiological culture. Then, 5% topical methyl aminolevulinate (MAL) as the prodrug for the photosensitizer Pp IX will be applied (5 x 10cm in the right groin) and followed by irradiation of the area with day light.

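### PDT always goes to the right groin and the antisepsis-only control is always the other groin, so the treated-versus-control comparison after antisepsis confounds side with PDT

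*Combined protocol and SAP*

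**What the plan says.** The treated side is named three times for each arm, and it is the right groin every time.

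- **Group A (MAL).** Section 5.2: the cream "will be applied (5 x 10cm in the right groin) and the photodynamic process will be started". Section 8.1: it "will be applied under occlusion in the right groin of the patient". Section 8.3.2: it "will be applied (5 x 10cm in the right groin) and followed by irradiation of the area with day light".
- **Group B (methylene blue).** Section 5.2: the product "will be applied for an area of 5 x 10cm in the right groin of the patient". Sections 8.1 and 8.3.2 repeat this.

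The comparator is set in section 2.5: "We will use for our control group without PDT the contralateral groin of the same participants". The Figure 1 footnote in section 5.2 agrees: "same participants as in the PDT group but swabs and skin antisepsis on the contralateral leg site". The word left is not used; it follows from contralateral.

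The documents disagree on who has this control. Section 5.2 says "we will take skin swabs before and after skin antisepsis without PDT on the contralateral site of all participants". Section 7.1.2 says "Skin antisepsis without PDT on the contralateral site of the first 10 participants". The Synopsis (Reference Intervention) says 10 participants.

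Allocation to arms is sequential and open label (section 5.1). No section randomises or alternates the treated side or gives a reason for choosing the right. Section 5.3, on minimising bias, does not mention side; the one potential bias it names is that healthy volunteers may differ from surgical patients. Section 10.3.2 describes the primary analysis as a descriptive before/after-PDT comparison. Section 10.3 names Fisher's exact, chi-squared and Wilcoxon rank sum tests.

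**The concern.** The hypothesis in section 10.1 is that PDT improves antisepsis. Testing it requires comparing PDT plus antisepsis with antisepsis alone, and only the contralateral groin supplies antisepsis alone. With the side fixed, everyone who contributes to that comparison has PDT on the right and control on the left. A systematic right-left difference in flora, antisepsis technique or sampling order then cannot be told apart from a PDT effect, and more participants do not help. Promising results are meant to lead to a trial in hip arthroplasty patients (sections 2.1 and 5.1), so this comparison matters beyond the pilot. Once treatment has been given, the confounding cannot be undone.

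**Working it through.** **1. Which comparisons does side enter?** Section 7.2.1 lists treated-groin scrapings before PDT (R0), after PDT but before antisepsis (R1), and after antisepsis (R2). The control groin is swabbed before (L0) and after (L2) antisepsis (Synopsis; section 5.2). Let d0 and d2 be the right-minus-left differences that would exist without PDT, before and after antisepsis.

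| Comparison | What it estimates | Side enters? |
|---|---|---|
| R2 − R0 (section 10.3.2) | PDT and antisepsis together | No |
| R1 − R0 | PDT without antisepsis | No |
| R2 − L2 | what PDT adds to antisepsis, plus d2 | Yes |
| (R2 − R0) − (L2 − L0) | what PDT adds to antisepsis, plus (d2 − d0) | Only as far as d2 differs from d0 |

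The first two comparisons are free of side but cannot show that PDT adds to antisepsis. The third can, but carries the whole of d2. The fourth removes a side difference that persists unchanged through antisepsis. It does not remove one that arises later, and it over-corrects if antisepsis itself evens out the two sides. Growth is graded only +, ++ or +++ (section 8.2.1, Microbiology), so changes adjust only roughly. The plan specifies neither the third nor the fourth comparison.

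**2. Bias in R2 − L2.** Input: an assumed additive difference d in the no-growth rate; the documents give none.

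- Fixed side: bias = d. For d = 10, 20 and 30 points, the bias is 10, 20 and 30 points at any n. With 10 participants, 10 points is 1 person and 20 points is 2.
- Simple randomisation of side: mean bias 0, SD = d/√n. At n = 10: 10/√10 = 3.2, 20/√10 = 6.3, 30/√10 = 9.5 points. At n = 20: 2.2, 4.5 and 6.7 points.
- Balanced list, 5 right and 5 left: (5d − 5d)/10 = 0.

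**3. If the effect is not additive.** The earlier MAL pilot reported complete sterilisation (section 2.1). Suppose treated groins show 100% no-growth on either side, and untreated groins pL (left) and pR (right). Fixed side gives 100 − pL; a balanced list gives 100 − (pL + pR)/2. The gap is (pR − pL)/2 = d/2, so 10 to 20 points becomes 5 to 10 points, or 0.5 to 1 participant of 10, relative to the effect averaged over sides.

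**4. False-positive rates.** These are illustrative: no PDT effect, sides independent within a person, exact McNemar test at two-sided 0.05. The plan does not name this test. P(growth on right only) = pR(1 − pL) and P(growth on left only) = pL(1 − pR), where p is now the positivity rate. For 50% left and 30% right these are 0.15 and 0.35.

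| Positive, left vs right | n | Fixed side | Balanced side |
|---|---|---|---|
| 50% vs 50% | 10 | 0.90% | 0.90% |
| 50% vs 50% | 20 | 2.26% | 2.26% |
| 50% vs 40% | 10 | 1.54% | 0.83% |
| 50% vs 40% | 20 | 4.96% | 2.13% |
| 50% vs 30% | 10 | 3.86% | 0.65% |
| 50% vs 30% | 20 | 15.07% | 1.76% |
| 60% vs 30% | 10 | 9.51% | 0.55% |
| 60% vs 30% | 20 | 33.98% | 1.34% |

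For a continuous measure with a side shift of 0.5 SD of the within-pair difference, a simulated signed-rank test (4,000 runs) gives about 26% fixed against 3% balanced at n = 10, and 56% against 3% at n = 20. With no side difference, fixed and balanced agree.

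**5. Sample size.** The stated 20 (section 10.2) cannot be reproduced, because no power, effect size, SD or rate is given. Nothing here depends on it, and the fix does not change it.

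**6. Who has a control.** Section 2.7 puts the first ten enrolled in group A. If section 7.1.2 governs, group B has no control groin and the comparison in question exists only in group A. If section 5.2 governs, it exists in both arms.

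**The case against.** A reader might infer that every right-left difference is counted as PDT effect throughout the trial. The documents do not support that. The primary analysis is a before/after comparison within the treated groin, and the control side does not enter it. Both groins are also swabbed before antisepsis, so a baseline imbalance would be visible and could be partly removed by comparing changes.

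A reader might also infer that a fixed side unmasks the laboratory through specimen labels. Stored isolates and biological material carry coded names (sections 12.2 and 12.6). Labels on the fresh swabs are not described, so the point cannot be made. Nor would randomising the side blind the operator of an open-label study.

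It is fair to add that no right-left data exist, that the one-for-one transfer assumes additivity, that the false-positive rates use tests outside the plan, and that this is a pilot of 20 volunteers described as descriptive.

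All of this stands and limits the point. It does not remove it: a before/after contrast in one groin cannot show that PDT improves on antisepsis, no baseline-adjusted paired comparison is planned, and baseline swabs cannot correct a difference that arises after them, such as one from antisepsis technique, sampling order or recolonisation.

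**Conclusion.** The point holds for the treated-versus-control comparison after antisepsis, and only there. Side and PDT are fully confounded in the one contrast that can answer section 10.1, and the plan neither allocates side at random nor specifies a baseline-adjusted paired analysis. The size is unknown and is zero if the groins do not differ. For an assumed difference of 10 to 20 points, the distortion is 10 to 20 points if additive, or 5 to 10 points if PDT sterilises either side completely. Whether this concerns one arm or both depends on the unresolved conflict over who has a control groin. For a descriptive pilot this is a minor to moderate weakness: a recommended change, justified mainly because the remedy costs almost nothing.

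**What to change.** 1. In sections 5.2, 8.1 and 8.3.2, replace the fixed right side with the groin allocated by a prepared random list, 5 right and 5 left within each arm that has a control groin. The other groin is the control.
2. Record the treated side in the eCRF.
3. In section 10.3, specify the treated-versus-control comparison as a within-person difference in change: after antisepsis minus the pre-PDT swab in the treated groin, against after antisepsis minus the pre-antisepsis swab in the control groin. Use a paired method in place of the rank sum test.
4. Reconcile the Synopsis and sections 5.2 and 7.1.2 on which participants have the control groin.
5. If there is a practical reason to keep one side, state it and list side as a limitation in section 5.3.

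Cost: a list of 20 lines (10 if only group A has a control), one eCRF field and wording changes before the first participant. There are no extra participants, visits or swabs if the control covers the participants already intended.
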